12 ANALYSIS PLAN

In general, descriptive statistics generated for an endpoint will be based upon the type of parameter (i.e., whether the data is categorical or continuous) being analyzed. For categorical parameters, the statistics used to summarize the data descriptively include sample size, number in the category, and percent in the category. For continuous parameters, sample size, mean, median, standard deviation, minimum, and maximum will be presented.

Analysis assumptions will be periodically reviewed during study conduct for deviations from analysis assumptions or the presence of outliers. The statistical methods should only be modified if there is a significant risk that the validity of the results can be substantively impacted. Because the study is open label, any discussion of analysis assumptions should not be based on review of any results by treatment group.

12.1 Subject Evaluability

Final subject evaluability must be determined prior to locking the database, based upon the Deviations and Evaluability Plan.

12.2 Analysis Sets

The Full Analysis Set (FAS) will include all eyes for enrolled subjects who are bilaterally implanted with the test or comparator IOL. The FAS will be the primary analysis set for effectiveness and will be used for all safety analyses.

12.3 Demographic and Baseline Characteristics

Demographic and baseline characteristics will be summarized by treatment group and overall. Counts and percentages will be presented for categorical variables such as sex, categorized age group (< 65 years; \geq 65 years), race, and ethnicity. The number of values, mean, standard deviation, median, and minimum, and maximum values will be presented for continuous baseline variables.

12.4 Effectiveness Analyses

12.4.1 Analysis of Primary Effectiveness Endpoints

The co-primary effectiveness objectives are:

- 1. To demonstrate that Clareon Vivity/Vivity Toric IOL is non-inferior to Clareon Monofocal/Clareon Toric IOL in mean binocular photopic best corrected distance visual acuity (BCDVA) at 3 to 6 months (90 to 180 days) postoperatively.
- To demonstrate that Clareon Vivity/Vivity Toric IOL is superior to Clareon Monofocal/Clareon Toric IOL in mean binocular photopic distance corrected intermediate visual acuity (DCIVA) (66 cm from spectacle plane) at 3 to 6 months (90 to 180 days) postoperatively.

The corresponding primary effectiveness endpoints are

- Binocular photopic BCDVA (logMAR) at 4 m.
- Binocular photopic DCIVA (logMAR) at 66 cm.

12.4.1.1 Statistical Hypotheses

The null and alternative hypotheses for the first primary effectiveness endpoint are:

Status: Approved, Version: 1.0 Approved Date: 13 Mar 2023

 $H_{0}: \mu_{Test} - \mu_{Comparator} \geq \Delta$ $H_{1}: \mu_{Test} - \mu_{Comparator} < \Delta$

where μ_{Test} and $\mu_{Comparator}$ are the means for binocular BCDVA for test (Clareon Vivity/Vivity Toric IOL) and comparator (Clareon Monofocal/Clareon Toric IOL), respectively, at 3 to 6 months (90 to 180 days) postoperatively, and Δ is the noninferiority margin set at 0.1 logMAR.

The null and alternative hypotheses for the second primary effectiveness endpoint are:

 $H_{0}: \mu_{Test} \geq \mu_{Comparator}$ $H_{1}: \mu_{Test} < \mu_{Comparator}$

where μ_{Test} and $\mu_{Comparator}$ are the means for binocular DCIVA for test (Clareon Vivity/Vivity Toric IOL) and comparator (Clareon Monofocal/Clareon Toric IOL), respectively, at 3 to 6 months (90 to 180 days) postoperatively.

12.4.1.2 Analysis Methods

The FAS will be used for the primary statistical analyses for both endpoints.

Analysis of the first primary endpoint (noninferiority for binocular BCDVA) will be based on a two-sample t-test assuming equal variances with testing based on a one-sided lower tailed test conducted at the 0.05 significance level. A corresponding two-sided 90% confidence interval for the difference in means (Clareon Vivity/Vivity Toric IOL minus Clareon/Clareon Toric IOL) will be presented. Noninferiority is demonstrated if the one-sided p-value for the t-test is less than 0.05 or, equivalently, the upper limit of the two-sided 90% confidence interval is less than the noninferiority margin. A two-sided 95% confidence intervals will also be provided for descriptive purposes.

Analysis of the second primary endpoint (superiority test for binocular DCIVA) will be based on a two-sample t-test assuming equal variances with testing based on a one-sided lower tailed test conducted at the 0.05 significance level. A two-sided 95% confidence interval for the difference in means (Clareon Vivity/Vivity Toric IOL minus Clareon/Clareon Toric IOL) will be presented.

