8 STUDY POPULATION

The study population consists of male and female subjects (18 years or older at the time of participation in the study) with previous bilateral implantation of Clareon Vivity/Clareon Vivity Toric or Clareon Monofocal/Clareon Toric IOLs for at least 3 months and up to 6 months (90 to 180 days) after second eye implant. It is aimed to enroll (consent) approximately 210 subjects at up to 12 sites in the United States, with a target of 190 subjects completing the study. The investigators and sites should also target equal numbers of subject in each group: Clareon Vivity/Clareon Vivity Toric or Clareon Monofocal/Clareon Toric, if possible. This is recommended but not required. Site-specific targets will vary based upon individual site capabilities. Estimated time needed to recruit subjects for the study is approximately 4 months; however, unanticipated circumstances may shorten or lengthen this time and would not require amendment of this protocol. Because a 9.5% screening failure rate is expected, approximately 210 subjects are expected to be enrolled.

This protocol allows enrollment of the following vulnerable population(s), with associated justification for each population:

Elderly – It is appropriate to include the elderly in this clinical study, as IOL implantation is intended to treat age-related cataract formation and is common to this population.

The elderly will be protected through the informed consent process, which will include any risks specific to the elderly subjects, as well as any specific responsibilities associated with their participation. In addition, an IRB/IEC will review and approve the inclusion of elderly subjects in this clinical study prior to enrollment of elderly subjects. Any specific requirements imposed by the IRB/IEC regarding participation of elderly subjects will be

implemented and documented, as appropriate. Upon conclusion of the clinical study, all subjects, including elderly subjects, will return to standard medical care for ongoing conditions.

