8.1 Inclusion Criteria

Written informed consent must be obtained before any study specific assessment is performed. Upon signing informed consent, the subject is considered enrolled in the study.

Subjects eligible for inclusion in this study must fulfill **all** of the following criteria:

- 1. Subject must be able to understand and sign an IRB/IEC approved Informed Consent form.
- 2. Willing and able to attend all scheduled study visits as required per protocol.
- Adults (18 years or older at the time of participation in the study) with previous bilateral implantation of Clareon Vivity/Clareon Vivity Toric or Clareon Monofocal/Clareon Toric IOLs for at least 3 months and up to 6 months after second eye implant.

The IOL spherical power must be within the 10.0 to 30.0 D range in both eyes and for both lens types. If a Toric lens was used, the cylinder power at the IOL plane must be in the range +1.50 to +3.75 Diopters in 0.75 D increments for each eye.

A subject may have a Toric lens in one eye and a non-Toric in the fellow eye as long as the IOL type is matched (e.g., Clareon Vivity/Vivity Toric or Clareon Monofocal/Monofocal Toric).

4. Documented medical history and required preoperative baseline information available for retrospective data collection.

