9.3 Treatment Assignment / Randomization

Only after signing the ICF, a subject will be assigned a subject number by the electronic data capture system. This study is not randomized.

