12.4.2.2 Analysis Methods

The FAS will be used for the primary statistical analyses for both endpoints.

Analysis of the first secondary endpoint (binocular DCNVA) will be based on a two sample ttest assuming equal variances with testing based on a one-sided lower tailed test conducted at the 0.05 significance level. A two sided 95% confidence interval for the difference in means (Clareon Vivity/Vivity Toric IOL minus Clareon/Clareon Toric IOL) will also be presented.

Analysis of the second secondary endpoint (Q1 for IOLSAT) will be based on a Chi-squared test of two proportions with testing based on a one-sided upper tailed test carried out at the 0.05 significant level. The proportion of subjects who respond "Never" to Q1 of the spectacle use questionnaire (IOLSAT) in each group will be presented.

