4 EFFECTIVENESS ANALYSIS STRATEGY

A success on co-primary effectiveness endpoints would be indicated by successful outcomes on both 2 of these endpoints (2 hypothesis tests). A total of four hypothesis tests will be conducted to address the co-primary and secondary objectives of the study. [REDACTED]

[REDACTED]

[REDACTED]

[REDACTED]

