4.3.1.2 Mean Binocular photopic DCIVA (logMAR) at 66 cm

Analysis of the second primary effectiveness endpoint (DCIVA) will be based on a two-sample t-test assuming equal variances, with a type I error rate of 5%, 1-sided. The difference in means (Vivity IOL minus Monofocal IOL) and the associated two-sided 90% confidence interval will be presented. Superiority is demonstrated if the one-sided p-value for the t-test is less than 0.05 or, equivalently, the upper limit of the two-sided 90% confidence interval is less than 0. A two-sided 95% confidence interval will also be provided for descriptive purposes.

In addition, the descriptive statistics (number and percentage in the category) will be provided for each IOL group described in Section 4.3.1.1.

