4.3.2.1 Mean Binocular photopic DCNVA (logMAR) at 40 cm

[figure not shown]
Analysis of the first secondary effectiveness endpoint (DCNVA) will be based on a two-sample t-test assuming equal variances, with a type I error rate of 5%, 1-sided. The difference in means (Vivity IOL minus Monofocal IOL) and the associated two-sided 90% confidence interval will be presented. Superiority is demonstrated if the one-sided p-value for the t-test is less than 0.05 or, equivalently, the upper limit of the two-sided 90% confidence interval is less than 0. A two-sided 95% confidence interval will also be provided for descriptive purposes.

[figure not shown]
In addition, the descriptive statistics (number and percentage in the category) will be provided for each IOL group described in Section 4.3.1.1.

[figure not shown]
4.3.2.2 Proportion of subjects who respond “Never” to Q1 of the spectacle use questionnaire (IOLSAT)

[figure not shown]
A two-sided 90% confidence interval for the difference in proportions (Vivity IOL – Monofocal IOL) will be calculated using the Miettinen-Nurminen method (1985), and Vivity IOL will be determined to be superior to Monofocal IOL if the lower boundary of the confidence interval is greater than zero. This is equivalent to using a type I error rate of 5%, 1-sided. A two-sided 95% confidence interval will also be provided for descriptive purposes.

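### The study is nonrandomised, but the legible decision rules for BCDVA, DCIVA and DCNVA are unadjusted t-tests, so reading the result as a lens effect counts any group difference in predictors of acuity as lens effect

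*Protocol*

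**What the plan says.** Protocol 9.3 states "This study is not randomized", and SAP 1.3 agrees. Protocol 7.1 describes subjects who received their lenses before enrolment.

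The acuity decision rules are as follows.

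- **BCDVA (noninferiority, margin 0.1 logMAR) and DCIVA (superiority):** under Protocol 12.4.1.2, each analysis "will be based on a two-sample t-test assuming equal variances", one-sided at 0.05. SAP 4.3.1.1 keeps the t-test for BCDVA. For DCIVA, SAP 4.3.1.2 says "Superiority is demonstrated if the one-sided p-value for the t-test is less than 0.05", or equivalently if the upper 90% confidence limit is below zero.
- **DCNVA (first secondary):** Protocol 12.4.2.2 says the analysis "will be based on a two sample ttest assuming equal variances". SAP 4.3.2.1 says "Analysis of the first secondary effectiveness endpoint (DCNVA) will be based on a two-sample t-test assuming equal variances".

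No legible sentence names a covariate, stratum, weight or match for these rules. Baseline characteristics are tabulated by group (Protocol 12.3, SAP 3). Sites are asked to aim for equal numbers per lens group, but "This is recommended but not required" (Protocol 8). On the co-primaries, SAP 4 says "A success on co-primary effectiveness endpoints would be indicated by successful outcomes on both 2 of these endpoints".

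**The concern.** The hypotheses in Protocol 12.4.1.1 and 12.4.2.1 and SAP 4.2 concern mean acuity in two groups. The objectives in Protocol 12.4.1 and 12.4.2 are worded differently: one lens is to be shown noninferior or superior to the other. A raw difference in means answers the second question only if the groups are alike in everything else that predicts acuity. Without randomisation, nothing in the design secures that.

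Age, sex, corneal shape, eye length and timing within days 90 to 180 may differ between people who received an extended-vision lens and people who received a monofocal one. A baseline table shows such a difference but does not correct for it.

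For BCDVA both false claims and lost power matter, because only 0.06 logMAR separates the expected difference (0.04) from the margin (0.10). DCIVA and DCNVA have ample power, so for them the issue is mainly a false claim of lens effect.

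**Working it through.** **Inputs.** SD 0.14; 95 evaluable subjects per arm; BCDVA margin 0.10 and expected difference 0.04; DCIVA difference 0.085; DCNVA difference 0.14 (Protocol 12.8, SAP 7). One-sided alpha 0.05 (Protocol 12.4.1.2, 12.4.2.2). Degrees of freedom 95 + 95 − 2 = 188.

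**Reproducing the plan.** SE = 0.14 × √(2/95) = 0.0203 logMAR. The critical t is 1.653.

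- BCDVA: noncentrality (0.10 − 0.04)/0.0203 = 2.95, power 0.903. The plan states 90%.
- DCIVA: power 0.994. The plan states > 98%.
- DCNVA: power > 0.999. The plan states > 99%.

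The plan's powers are therefore those of an unadjusted comparison with no allowance for confounding. Noninferiority is declared when the observed difference is below 0.10 − 1.653 × 0.0203 = 0.066, and superiority when it is below −0.034.

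**Effect of a bias b (assumed; the documents give none).** If a factor differs by d SD between groups and correlates r with acuity, b = d × r × 0.14. For example, d = 0.25 and r = 0.1 gives 0.0035; d = 0.25 and r = 0.2 gives 0.007; d = 0.5 and r = 0.3 gives 0.021. The value 0.02 below is a round figure close to the last.

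- Error for the lens-effect null, b favouring the test lens: probability that a noncentral t with noncentrality b/0.0203 exceeds 1.653. The null boundary is a true difference of 0.10 for BCDVA and 0 for DCIVA and DCNVA.
- BCDVA power, b against the test lens: the same probability with noncentrality (0.06 − b)/0.0203.

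| b (logMAR) | Error, b favours test lens | BCDVA power, b against test lens |
|---|---|---|
| 0 | 5% | 90% |
| 0.0035 | 7.0% | 87% |
| 0.007 | 9.7% | 83% |
| 0.02 | 25% | 62% |

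With b = 0.02 against the test lens, DCIVA power is still 94% and DCNVA power above 99.9%. Since both co-primaries must succeed, overall false success cannot exceed the error of the test whose null is true.

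**Does adjustment help?** In simulation with d = 0.5 and r = 0.3, the t-test error was 27% and the error of a linear model containing that factor was 5.0%. This shows only that the model works when the factor is recorded and its effect is linear.

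**Power cost of adjustment.** With five covariates (df 183), adjusted SE = 0.0203 × √(1 − R²y)/√(1 − R²g). R²g is the share of group membership that the covariates explain, and R²y the share of acuity variance; both are assumed.

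| R²g | BCDVA power, R²y = 0 | BCDVA power, R²y = 0.1 |
|---|---|---|
| 0.1 | 87% | 90% |
| 0.2 | 84% | 87% |
| 0.3 | 79% | 83% |

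DCIVA power stays at about 97% or more throughout.

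**The case against.** - **The tests are valid as written.** This stands. The hypotheses are about group means, and the t-test keeps one-sided 5% for those. A reader might infer that the plan's stated error rate is wrong; the documents do not support that. The inflation applies only to the lens-effect reading, which the objectives invite.
- **The design already limits confounding.** This stands in part. Shared eligibility rules restrict co-morbidity, corneal refractive surgery, monovision targets, PCO, amblyopia, lens power and time since implant (Protocol 8.1, 8.2). Refraction and acuity assessors are masked, and all three acuities are best or distance corrected. But the co-morbidity rule rests on investigator opinion, masking limits measurement bias and not confounding, and correction removes only refractive error.
- **An adjusted analysis may already exist.** This stands. SAP 4, 4.3.1, 4.3.1.1, 4.3.2 and 4.6 contain redactions. The text between 4.3.2.2 and 4.6, including Table 4-1, and section 6 are not shown. A reader might infer that no adjustment is planned; that cannot be said. It does not change the legible rule, because the protocol gives all three rules in full.
- **The magnitudes are hypothetical.** This stands. No passage shows that the named factors predict corrected binocular acuity in this screened population, or that they differ between groups.
- **This is a study to augment parent-model data after registration, so a supportive adjusted analysis would be enough.** This is reasonable as a minimum, provided a lens-effect claim must then agree with both analyses.

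**Conclusion.** The point holds for the legible decision rules. For BCDVA, DCIVA and DCNVA they are unadjusted comparisons of groups that were not randomised, so confounding by any predictor of acuity passes straight into the estimate if that estimate is read as a lens effect.

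The size is unknown. Errors of 7% to 25% and BCDVA powers of 62% to 87% correspond to assumed biases of 0.0035 to 0.02 logMAR, with SD 0.14 and 95 per arm. A reader might infer that the bias favours the test lens; nothing in the documents supports a direction.

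This should be fixed but does not invalidate the study. The factors needed are largely collected already, and an adjusted model is most credible if it is fixed before unmasking. IOLSAT Q1 is also compared without adjustment, but it is outside this point because its group proportions are not given.

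**What to change.** Before unmasking, prespecify for BCDVA, DCIVA and DCNVA an adjusted mean difference from an equal-variance linear model. Include IOL group, age, sex, toric lens in at least one eye (yes/no), preoperative keratometry (mean of both eyes) and days from second implant to Visit 1. Keep the 90% confidence interval rule and the margin.

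- **Role.** Preferably this is the decision estimate, with the planned t-test as the unadjusted sensitivity analysis. At minimum, report it beside the t-test and require any lens-effect claim to be supported by both. If an unshown adjusted model already exists, use that one.
- **Covariates.** Fix the list in advance and do not let the amount of missing data decide which factors stay. Keep a subject with a missing covariate by using an indicator. Few should be missing, since inclusion criterion 4 requires "Documented medical history and required preoperative baseline information available for retrospective data collection". In simulation, with d = 0.25, r = 0.2 and d = 0.5, r = 0.3, the indicator gave errors of 5.0% to 5.4% at 5% missing and 5.3% to 6.3% at 10% missing. No outcome is imputed.
- **Site.** Add a site-adjusted sensitivity analysis. Putting site in the decision model could be costly: if every site had a 70/30, 80/20 or 90/10 lens mix, BCDVA power would be 85%, 76% or 55%.
- **Limits to state.** Adjustment covers measured factors only, medical history is not in the eCRF (Protocol 10.2.2), and site confounding is addressed only by the sensitivity analysis.
- **Places to change together.** Protocol Summary (analysis rules and power table); Protocol 12.4.1.2, 12.4.2.2 (DCNVA) and 12.8; SAP 4.3.1.1, 4.3.1.2, 4.3.2.1 and 7.

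The cost is a short amendment, SAP wording and minor programming, with no added visit or enrolment. Restate BCDVA power using the 79% to 90% range shown above.

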4.3.1.1 Mean Binocular photopic BCDVA (logMAR) at 4 m

Analysis of the first primary effectiveness endpoint (BCDVA) will be based on a two-sample t-test assuming equal variances, [REDACTED]. The difference in means (Vivity IOL minus Monofocal IOL) and the associated two-sided 90% confidence interval will be presented. Noninferiority is demonstrated if the one-sided p-value for the t-test is less than 0.05 or, equivalently, the upper limit of the two-sided 90% confidence interval is less than the noninferiority margin. A two-sided 95% confidence interval will also be provided for descriptive purposes.

[REDACTED]

In addition, the following descriptive statistics (number and percentage in the category) will be provided for each IOL group:

- logMAR categories: the number and percentage of eyes (for monocular endpoints)/subjects (for binocular endpoints) with visual acuity of
 - 0.0 logMAR or better: ≤ 0.00 logMAR
 - 0.1 logMAR or better: ≤ 0.10 logMAR
 - 0.2 logMAR or better: ≤ 0.20 logMAR
 - 0.3 logMAR or better: ≤ 0.30 logMAR
- Snellen categories: the number and percentage of eyes (for monocular endpoints)/subjects (for binocular endpoints) with visual acuity of
 - 20/20 Snellen or better: ≤ 0.04 logMAR
 - 20/25 Snellen or better: ≤ 0.14 logMAR
 - 20/32 Snellen or better: ≤ 0.24 logMAR
 - 20/40 Snellen or better: ≤ 0.34 logMAR

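### The pooled t-test for the three acuity endpoints may drift from its one-sided 5% level if arm sizes and SDs both turn out unequal; naming Welch's test now removes that risk at almost no cost

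*Protocol*

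**What the plan says.** Protocol 12.4.1.2 tests both co-primary endpoints with a "two-sample t-test assuming equal variances", one-sided and lower-tailed at the 0.05 level. Protocol 12.4.2.2 does the same for DCNVA. The SAP agrees in all three places:

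- 4.3.1.1: "Analysis of the first primary effectiveness endpoint (BCDVA) will be based on a two-sample t-test assuming equal variances". The words after the comma are redacted.
- 4.3.1.2, for DCIVA: "t-test assuming equal variances, with a type I error rate of 5%, 1-sided".
- 4.3.2.1: "Analysis of the first secondary effectiveness endpoint (DCNVA) will be based on a two-sample t-test assuming equal variances".

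The decision rule for BCDVA follows from this standard error: "Noninferiority is demonstrated if the one-sided p-value for the t-test is less than 0.05", or equivalently the upper 90% confidence limit lies below the margin. In protocol 12.4.1.1, Δ "is the noninferiority margin set at 0.1 logMAR".

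Protocol 12.8 and SAP Section 7 plan 190 evaluable subjects, 95 per arm, with one SD of 0.14 for every acuity endpoint. Protocol 9.3 states that there is no randomisation. Protocol Section 8 asks investigators and sites to aim for equal group sizes where they can, then adds: "This is recommended but not required".

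The opening of protocol Section 12 provides for periodic review of analysis assumptions and allows methods to change if validity is seriously at risk. It names no trigger and no alternative test, and it rules out basing that discussion on results by treatment group.

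**The concern.** The pooled standard error weights the two sample variances by arm size, whereas the true variance of the difference divides each variance by its own arm size. The two agree when the arms are equal in size or the SDs are equal. If the smaller arm has the larger SD, the pooled standard error is too small and the test rejects too often. If the larger arm has the larger SD, it is too large and the test loses power.

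Nothing in the design fixes the arm ratio, because subjects arrive already implanted and site-level balance is optional. Nothing ensures equal SDs either: the groups carry different optical designs and were not formed by chance.

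Both co-primary decisions and the first secondary decision rest on this standard error. The plan's review of assumptions cannot detect the problem before unmasking, because comparing two arm variances needs results by group. A change of test after unmasking would be post hoc.

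**Working it through.** **Inputs from the documents.** Margin 0.10, expected BCDVA difference 0.04, common SD 0.14, 95 per arm, one-sided 5% (protocol 12.4.1 and 12.8; SAP Section 7).

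**Assumed inputs.** The documents give no arm-specific SDs and no expected imbalance. The SD pairs and the unequal splits of 190 below are assumptions.

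**1. The plan's own figure.** SE = 0.14 × √(2/95) = 0.0203. Noncentrality = (0.10 − 0.04)/0.0203 = 2.95. With 188 degrees of freedom the noncentral t gives 90.3% power (normal approximation 90.5%). The stated 90% reproduces.

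**2. Formula.** Write n₁, s₁ and n₂, s₂ for the arm sizes and true SDs.

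- True variance of the difference: V = s₁²/n₁ + s₂²/n₂
- Pooled variance: s_p² = [(n₁−1)s₁² + (n₂−1)s₂²]/(n₁+n₂−2)
- Variance the pooled test targets: V_p = s_p²(1/n₁ + 1/n₂)
- Approximate one-sided error: Φ(−1.645·k), with k = √(V_p/V)

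If n₁ = n₂ then V_p = V and k = 1 whatever the SDs.

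**3. One case in full.** Arms 70 (SD 0.15) and 120 (SD 0.10).

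- V = 0.0225/70 + 0.0100/120 = 0.000405
- s_p² = (69 × 0.0225 + 119 × 0.0100)/188 = 0.01459
- V_p = 0.01459 × (1/70 + 1/120) = 0.000330
- k = √(0.000330/0.000405) = 0.903
- Error ≈ Φ(−1.645 × 0.903) = Φ(−1.485) = 6.9%

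Simulation gives 6.8%.

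**4. Range.** Simulated one-sided error at the null boundary, at least 400,000 trials per row. SDs are in the same order as the arm sizes.

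| Arm sizes | SDs | k | Pooled | Welch |
|---|---|---|---|---|
| 95/95 | 0.14/0.14 | 1.000 | 5.0% | 5.0% |
| 95/95 | 0.16/0.12 | 1.000 | 5.0% | 5.0% |
| 85/105 | 0.16/0.12 | 0.971 | 5.5% | 5.0% |
| 70/120 | 0.15/0.13 | 0.963 | 5.7% | 5.0% |
| 80/110 | 0.15/0.10 | 0.941 | 6.1% | 5.0% |
| 63/127 | 0.16/0.12 | 0.909 | 6.7% | 4.9% |
| 70/120 | 0.15/0.10 | 0.903 | 6.8% | 5.0% |
| 70/120 | 0.10/0.15 | 1.107 | 3.4% | 5.0% |

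At 95/95 the pooled test also holds about 5% with SDs of 0.14 and 0.07. The t statistic is unaffected by a shift in the null value, so the same rates apply to the DCIVA and DCNVA superiority tests at a true difference of zero.

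**5. BCDVA power at a true difference of 0.04.**

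| Arm sizes | SDs | Pooled | Welch |
|---|---|---|---|
| 95/95 | 0.14/0.14 | 90.3% | 90.3% |
| 70/120 | 0.14/0.14 | 88.4% | 88.3% |
| 70/120 | 0.15/0.10 | 93.2% | 90.6% |
| 127/63 | 0.16/0.12 | 85.9% | 89.2% |

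In the third row the pooled test's higher power reflects its excess type I error. In the fourth row the pooled test is conservative and loses 89.2 − 85.9 = 3.3 points.

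**The case against.** The strongest reply is that the problem needs two departures from plan together, and the documents predict neither. The study-level target is about 95 per arm throughout, and the sentence making balance optional concerns what investigators and sites should aim for. At the target, the pooled test is correct even with a 2:1 SD ratio. All of this stands. A reader might infer that the noninferiority test as planned fails to hold 5%; the documents do not support that.

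The larger figures also depend on assumed SDs. The pair 0.15/0.10 at 70/120 implies a pooled SD of √0.01459 = 0.12, below the plan's 0.14. At 85/105 with 0.16/0.12 the pooled SD is √0.0194 = 0.14, as planned, and the error is 5.5%. This stands too: unless the imbalance approaches 2:1 or the SDs differ strongly, the drift is modest. A reader might also suppose that the way patients came to receive each lens makes unequal SDs likely. The documents say only that subjects were previously implanted and not randomised; they give no evidence on arm-specific spread.

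Two further replies carry less weight. First, the protocol does provide for review of assumptions; but without by-group results that review cannot compare variances. Second, redacted SAP text may contain a supporting analysis, so one cannot say that nothing else is planned; but the stated primary test is pooled in both documents.

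Finally, the pooled t-test is conventional and consistent with the common-SD power calculation, and in a nonrandomised comparison confounding is probably the larger threat. That bears on priority and supports treating this as minor.

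**Conclusion.** The point holds in conditional form. At the planned 95/95 there is no error-rate problem. If the arms and the SDs both turn out unequal, the one-sided 5% level may drift upward to 5.5% to 6.8%, or down to 3.4% with lost power, in the assumed cases at splits up to 70/120. The direction depends on which arm is smaller and which has the larger SD, and neither is known in advance. Welch's test stays at about 5.0% in all of these cases.

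The sizes rest on assumed SD pairs and splits and on normally distributed data. Severity is minor. The reason to act is that the choice must be made before unmasking and the safer option costs almost nothing.

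**What to change.** In protocol 12.4.1.2 and 12.4.2.2, and in SAP 4.3.1.1, 4.3.1.2 and 4.3.2.1, change the specification from equal variances to a two-sample t-test with unequal variances (Welch, Satterthwaite degrees of freedom). Carry the same wording into the protocol summary. Compute the 90% and 95% confidence intervals for the three acuity endpoints the same way, so that the p-value and the 90% interval still give the same decision.

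The cost is a wording change and one software option; sample size, visits and data collection are unaffected. With equal SDs, power is unchanged at 95/95 and falls by less than 0.1 point at 70/120. Where the pooled test would be inflated, Welch shows lower power only because it removes the excess type I error.
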